9.5.1.3.3 CEREBROSPINAL FLUID SAMPLING

Amyloid CSF is 1 of the 2 methods available at screening to determine subject eligibility for the study. (revised per Amendment 02) Subjects who undergo the eligibility CSF sample collection or who consent to the CSF longitudinal substudy will be encouraged to stay at the site after completion of LP for medical observation. CSF sample(s) will be collected by LP (gravity drip method only) after fasting (preferred), or at least 2 hours after the most recent meal.

CSF samples at Visit 13 should be collected while the subject is still on the study drug and before the other visit assessments. All ED CSF samples need to be taken no later than 7 days after the last dose of study drug. All CSF samples should be taken at approximately the same time of day as at the Screening Visit. (revised per Amendment 05)

Subjects who provide a CSF sample at Screening for amyloid eligibility purposes, but did not initially consent to the CSF longitudinal substudy may provide consent to the CSF longitudinal substudy at any point in time up to the CSF procedure at Visit 13 (or ED). INR results should be reviewed for subjects who consent to provide a CSF sample and are on concomitant anticoagulation/antiplatelet therapy, before LP; if they are assessed by the investigator to be at risk for bleeding, they are to be excluded from CSF collection. (revised per Amendment 01)

9.5.1.4 Pharmacokinetic, Pharmacodynamic, Pharmacogenomic, and Other Biomarker Assessments

9.5.1.4.1 PHARMACOKINETIC ASSESSMENTS

Blood samples will be collected for the determination of the concentrations of elenbecestat in all randomized subjects. Analyses of metabolite concentrations may be performed, depending on emerging data from other studies with elenbecestat. Samples from all subjects receiving active treatment will be analyzed. Placebo samples will be held in storage in the event that confirmatory analysis is requested. (revised per Amendment 03) Plasma concentrations of analytes will be quantified by liquid chromatography with tandem mass spectrometry methodology using a previously validated assay.

Blood samples will be collected as specified in [Table 4](#) and [Table 5](#). Two plasma PK samples will be obtained at each of the following visits: 1 sample at predose (trough) and another sample 1 to 6 hours postdose at Visits 3, 4, 6, 7, 9, and 11 and another sample 4 to 8 hours postdose at Visit 13 (or ED). Therefore, subjects or their study partners must be instructed not to take their study drug at home on the day the PK sampling is performed. Instead, subjects will take the study drug at the clinic after collection of the predose PK sample. At Visit 13 (or ED), the trough PK blood sample should be collected shortly before or after completing the LP for subjects participating in the CSF substudy. If the study drug is temporarily suspended, postdose PK samples will not be required. If at an ED Visit, the subject has already stopped study drug, postdose PK samples are not required. (revised per Amendment 05)

Blood will also be drawn where possible at the first report of an SAE or severe unexpected AE and at its resolution.

See the laboratory manual (to be supplied to study sites) for a description of the collection, handling, and shipping procedures for PK samples.

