- s: MRI scans are to include vMRI and fMRI sequences and will be read by an approved central reader. MRI imaging will be conducted on separate days from the scheduled visits. MRI imaging should be conducted within the 7 days before Visits 9 and 13. In the event of an Unscheduled Visit, the investigator in consultation with the medical monitor will determine whether or not a safety MRI should be conducted. If an ED Visit takes place, an MRI is to be conducted if not already performed during the preceding 90 days.
- t: Amyloid PET scanning (if subject has consented to optional substudy) will be performed with a locally approved amyloid β imaging agent (eg, Neuraceq, if available) or an agent under clinical investigation if no agents are approved locally; the imaging agent must remain unchanged for an individual subject throughout the study. An amyloid PET scan will only be performed at an ED Visit if the subject has been treated with study drug for at least 39 weeks and at least 6 months has elapsed since the prior amyloid PET scan was performed. (revised per Amendments 03 and 04)
- u: For subjects who consent to the tau PET longitudinal substudy, tau PET will be conducted at 24 months of treatment during the Core Study (or at the ED visit, provided the subject has received at least 39 weeks of study drug). At the 24 month timepoint (or at the ED visit), the amyloid and tau PET scans can be performed in either order but must be at least 48 hours apart. If the subject has also consented to the longitudinal CSF substudy, the longitudinal substudy assessments can be performed in any order, with at least 48 hours between each procedure. Tau PET scanning will be performed using a sponsor-supplied tau PET imaging agent, eg PI-2620. (revised per Amendment 04)
- v: Site staff will contact the subject or the study partner the day before the PK blood sampling to provide instructions that subjects must not take their study drug at home on the day of the PK blood sampling. During this telephone contact with the subject or the study partner, the site staff should document the time that the subject took their study drug that day, ie, the day before the PK blood sampling.

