- w: Two plasma PK samples will be obtained: 1 sample at predose (trough) and another sample 1 to 6 hours postdose at Visits 3, 4, 6, 7, 9, and 11 and another sample 4 to 8 hours postdose at Visit 13 (or ED). Therefore, subjects or their study partners must be instructed not to take their study drug at home on the day the PK sampling is performed. Instead, subjects will take the study drug at the clinic after collection of the predose PK sample. At Visit 13 (or ED), the trough PK blood sample should be collected shortly before or after completing the LP for subjects participating in the CSF substudy. If the study drug is temporarily suspended, postdose PK samples will not be required. If at an ED Visit, the subject has already stopped study drug, postdose

Table 5 Schedule of Procedures/Assessments in Study E2609-G000-302 (Revised per Amendments 04 and 05)

Phase	Randomization														
	Treatment												Follow-Up		UN Visit ^d
Visit ^a	2	3	4	5	6	7	8	9	10	11	12	13	ED ^b	14 ^c	
Day	1	15	29	57	85	183	274	365	456	547	638	729		757	813
Week	1	3	5	9	13	27	40	53	66	79	92	105		109	117
Weeks elapsed since 1st dose	0	2	4	8	12	26	39	52	65	78	91	104		108	116
Nominal months elapsed since 1st dose	0		1	2	3	6	9	12	15	18	21	24		25	27
Procedures/ Assessments															

PK samples are not required.

- x: PD and exploratory biomarker blood samples should be collected at fasting or at least 2 hours after the most recent meal and, as far as is feasible, samples should be taken at the same time of day at all visits. Samples should be taken predose at Visits 2, 3, 4, 6, 7, 9, 11, 13 (or ED), 14, and 15. (revised per Amendments 02 and 03)

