- y: For subjects who consent to participate in the CSF longitudinal substudy. Visit 13 (or ED) also includes blood PK and PD assessments and so the subject will be dosed at the clinic on these days. A CSF sample will be collected by LP between 4 and 8 hours postdose and at the same time of day as the subject's Screening LP (±1 hour). The CSF sample will be taken with the subject fasting (preferred) or at least 2 hours after the most recent meal. A gravity drip collection method must be used. If performed on the same day as the cognitive tests, the LP will be performed after the cognitive tests; the subject should rest and drink some fluid to hydrate after the cognitive tests and before the LP. Subjects will be encouraged to stay at the site after completion of LP for medical observation. The CSF sample will not be taken at the ED Visit if this visit occurs within 39 weeks of treatment or 3 months of a previous CSF sample. If at an ED Visit, the subject has already stopped study drug, then no dosing will take place, but the CSF sample will still be collected unless it was already collected within the past 3 months. Subjects receiving concomitant anticoagulation/antiplatelet therapy should have prothrombin time and INR (derived from prothrombin time) before LP; if they are assessed by the investigator to be at risk for bleeding, they are to be excluded from CSF collection. Note that subjects who are assessed by both amyloid PET and CSF are required to wait for a minimum of 48 hours between the 2 procedures. (revised per Amendment 01)
- z: Subjects reporting AEs relating to abnormal dreams, nightmares, or sleep terror will be questioned on the nature, frequency, and impact of these events.
- aa: AEs that may signal drug abuse potential require a more detailed follow-up through completion of a specific eCRF form (Possible drug abuse potential form/ questionnaire). Similarly, AEs reported during the first 4 weeks following the last dose of study drug that might indicate physical dependency also require a more detailed follow-up through completion of the same eCRF form. Categories and examples of AEs indicating signals of possible drug abuse are provided in [Appendix 3](#) and a more comprehensive list is provided in the eCRF Completion Guidelines. (revised per Amendments 01 and 03)

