Blood for immunologic assessments, (revised per Amendments 03 and 05) ^b	8		1×10 mL	7×10 mL	80 mL
Blood for PBMCs (revised per Amendment 05)	4	none	1×10 mL	3×10 mL	40 mL
Blood for immune status (revised per Amendment 03)	8	none	1×5 mL	7×5 mL	40 mL
AD diagnostics and exploratory biomarker (revised per Amendment 03)	1	1×6 mL	none	none	6 mL
PD and exploratory biomarker sample (revised per Amendments 01, 02, and 03)	10	none	1×12 mL	9×6 mL	66 mL
PK analysis (revised per Amendment 02)	7	none	none	14×2 mL	28 mL
Pharmacogenomic sample (revised per Amendments 01 and 02)	1	1×6 mL	none	none	6 mL
All blood samples, total volume collected (revised per Amendments 01, 02, 03, and 05)		25.8 mL	46.8 mL	298.9 mL	371.5 mL
CSF					
Amyloid eligibility	1	1×12 mL	none	none	12 mL
PD / PK (optional longitudinal substudy)	1	none	none	1×12 mL	12 mL

Note: Actual volumes may be less, based on regional differences in Central Laboratories.

AD = Alzheimer's disease, CMV = cytomegalovirus, CSF = cerebrospinal fluid, HSV1 = herpes simplex virus 1 (orolabial herpes), HSV2 = herpes simplex virus 2 (genital herpes), PBMCs = peripheral blood mononuclear cells, PD = pharmacodynamics, PK = pharmacokinetic, TFT = thyroid function Test.

a: The total volume includes all blood/CSF collection from Screening through Week 117 (Follow-up Visit) ; actual volume may vary based on local regulations. (revised per Amendment 02)

b: Immunological assessment samples not required for subjects randomized after 07 Sep 2018 - reducing total blood volume to 291.5 mL (revised per Amendment 05)

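### At Visit 13 (or ED), a CSF-substudy subject dosed on the lumbar puncture day cannot have a predose trough that is also drawn next to a lumbar puncture set at 4 to 8 hours postdose

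*Protocol*

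**What the plan says.** Section 9.5.1.4.1 and Table 5 footnote w schedule two plasma PK samples at each of seven visits. At Visits 3, 4, 6, 7, 9 and 11 these are "1 sample at predose (trough) and another sample 1 to 6 hours postdose". At Visit 13 (or ED) the second sample moves to 4 to 8 hours after the dose.

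The subject is to arrive undosed. Footnote v has staff telephone the day before with the instruction that "subjects must not take their study drug at home on the day of the PK blood sampling". At the clinic, "subjects will take the study drug at the clinic after collection of the predose PK sample".

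Both places then add a rule for the CSF substudy at Visit 13 (or ED). In Section 9.5.1.4.1 it reads: "At Visit 13 (or ED), the trough PK blood sample should be collected shortly before or after completing the LP". In footnote w it reads: "the trough PK blood sample should be collected shortly before or after completing the LP for subjects participating in the CSF substudy". Footnote y says these subjects are dosed at the clinic that day and that "A CSF sample will be collected by LP between 4 and 8 hours postdose".

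Three further statements bear on the point:
- Postdose PK samples are not required when study drug is temporarily suspended, or already stopped by the ED Visit (Section 9.5.1.4.1, footnote w).
- CSF is still collected at an ED Visit after drug has stopped, subject to footnote y's limits of 39 weeks of treatment and 3 months since the last CSF sample.
- PK samples from subjects on active treatment are analysed; placebo samples are held in storage (Section 9.5.1.4.1).

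**The concern.** On a dosed LP day, sites are given three timing rules: the trough comes before the dose, the trough is close to the LP, and the LP is hours after the dose. Any two can be kept together, but not all three. A site that puts the LP sentence first has two options. It can draw blood beside an LP done 4 to 8 hours postdose and label that sample a trough, or it can move the LP forward to before the dose and miss the CSF window. The first gives a mislabelled concentration and may lose the true Visit 13 trough. The second gives a CSF sample at the wrong time after dosing, at the only scheduled on-treatment CSF timepoint of the Core Study (Section 9.2.4).

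**Working it through.** The protocol gives no figure to reproduce here. The check is one of intervals, with the clinic dose at 0 h.

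**Inputs**
- Trough time T ≤ 0 h: predose, with the dose after it (Section 9.5.1.4.1; footnote w).
- LP time L, with 4 ≤ L ≤ 8 h (footnote y).
- Required closeness: |L − T| ≤ s, where s is the meaning of 'shortly'. No value is given.
- Visit 13 postdose PK sample time P, with 4 ≤ P ≤ 8 h. At the other six PK visits the window is 1 to 6 h (Section 9.5.1.4.1; footnote w).

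**Gap between trough and LP**
- Smallest gap: 4 − 0 = 4 h.
- Largest gap, for a trough drawn just before the dose: 8 − 0 = 8 h. An earlier trough makes the gap longer.
- With s assumed to be 0.5, 1, 2 or 3 h, no schedule satisfies all three rules. The first of the tried values that works is s = 4 h.

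**Does the following day's predose time help?** If once-daily doses are taken as 24 h apart, an LP at 4 to 8 h is 24 − 8 = 16 h to 24 − 4 = 20 h before the next predose time. It does not help.

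**Which sample could sit beside the LP?** The Visit 13 postdose window (4 to 8 h) is identical to the LP window (4 to 8 h), so |L − P| can be close to 0. The 1 to 6 h window used at the other visits would not cover the whole LP window. If the LP is paired with P and T stays predose, every rule can be met.

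**Visits without a dose.** If drug is suspended or already stopped at ED, there is no 0 h and no postdose sample is required. The one remaining PK sample can be drawn beside the LP, so the present sentence works for these subjects.

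**Size**
- PK visits: 3, 4, 6, 7, 9, 11 and 13, which is 7 visits and 7 troughs. PK samples: 2 × 7 = 14, matching the PK row of Table 6.
- One trough is 1/7 = 14.3% of a subject's troughs and 1/14 = 7.1% of the PK samples.
- Allocation is approximately 1:1 and placebo samples are stored, so about half of the CSF-substudy subjects contribute an analysed sample. The number in the substudy is not stated.

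**The case against.** The strongest reply is that a careful site will not lose the trough. It is told that the sample is predose, that the dose follows it, and to telephone ahead so that the subject comes in undosed. Predose blood for pharmacodynamics is also required at Visit 13 (Section 9.5.1.4.2; footnote x). A site that follows all of this has the trough, and its separate 4 to 8 hour sample already falls in the LP window. This limits the harm, so loss of the trough is a risk and not a certainty. It does not make the LP sentence possible to follow.

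A second reply is that the LP window is the wrong rule. Sections 9.1.2, 9.1.2.1 and 9.5.1.3.3 want CSF taken ahead of other Visit 13 assessments, so LP, trough beside it, then dose would be a coherent order. The text favours the other reading: the Visit 13 PK window matches the LP window exactly, and Table 9 footnote k repeats the 4 to 8 hour postdose LP for the Extension Phase. The sponsor should still confirm which was meant.

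A reader might infer that 'trough' is simply a slip and should be replaced by the postdose sample throughout. The documents do not support that. The sentence also covers ED, where a subject off drug has no postdose sample but may still give CSF. A blanket replacement would tie that LP to a sample that is not taken.

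A reader might also infer damage to the PK/PD results or the efficacy comparison. Section 9.7.1.7.1 plans population PK, which can use a postdose sample if its actual time is recorded. Section 9.7.1.7.2 works from model-derived exposure or CSF concentrations and does not call for a time-matched plasma and CSF pair.

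**Conclusion.** The instruction is wrong as written, and the severity is minor. For CSF-substudy subjects dosed at the clinic on the LP day, the predose trough is at least 4 hours from the LP, so the closeness rule cannot be met on any natural meaning of 'shortly'. The effect is confined to one PK sample per elenbecestat-arm CSF-substudy subject, at Visit 13 or a dosed ED Visit. Nothing in the documents links it to the primary comparison, the significance level or the sample size. The conclusion rests on the LP being done after the clinic dose on the same day, as footnote y states, and on 'shortly' meaning less than 4 hours. Subjects already off drug at ED fall outside it.

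**What to change.** Replace the LP sentence in Section 9.5.1.4.1 (at both places where that section appears in the document) and in Table 5 footnote w with a two-part rule:

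- *If the subject is dosed at the clinic on the LP day, collect the trough before the dose and collect the 4 to 8 hour postdose PK sample shortly before or after the LP.*
- *If no dose is given, because drug is suspended or already stopped at ED, collect the single PK sample shortly before or after the LP.*

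The sponsor should confirm that the postdose LP window is the intended one. The cost is one reworded sentence at each place. No visit, sample or analysis changes.

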9.5.1.4.2 PHARMACODYNAMIC, PHARMACOGENOMIC, AND OTHER BIOMARKER, ASSESSMENTS

[Table 2](#) lists PD, pharmacogenomic, and exploratory biomarker assessments. Key elements of these assessments are described below. (revised per Amendment 03)

Table 2 Planned Pharmacodynamic, Pharmacogenomic, and Other Biomarker Assessments (revised per Amendment 05)

Sample	Screening		Baseline		Treatment/Follow-up			
Whole Blood/ Plasma	PGx	Putative AD Diagnostic	PD	Example of Exploratory Biomarkers	PD	Example of Exploratory Biomarkers		
	ApoE ^a NAT2 ^b TREM2 ^b CD33 ^b EPHA1 ^b	microRNA tau:Aβ(1-42) Aβ42/Aβ40 ratio Aβ oligomers	Aβ(1-x)	NFL VILIP1 YKL-40 Tau	Aβ(1-x)	NFL VILIP1 YKL-40 Tau		
Sample	Eligibility		Baseline (CSF Substudy)		Treatment/Follow-up (CSF Substudy)			
CSF	CSF AD Biomarkers		PD	CSF AD Biomarkers	Example of Exploratory Biomarkers	PD	CSF AD Biomarkers	Example of Exploratory Biomarkers
	Aβ(1-42) Tau:Aβ(1-42) ratio		Aβ(1-x)	Aβ(1-42) tau p-tau (Subset) Aβ isoforms Aβ(1-40) Aβ(1-38)	NFL VILIP1 YKL-40 BDNF BACE1 Neurogranin	Aβ(1-x)	Aβ(1-42) tau p-tau (Subset) Aβ isoforms Aβ(1-40) Aβ(1-38)	NFL VILIP1 YKL-40 BDNF BACE1 Neurogranin

Aβ = amyloid beta, Aβ(1-x) = amyloid beta (1-x) (ie, the amyloid beta monomer from amino acid 1 to x [eg 1-42]), AD = Alzheimer's disease, ApoE = apolipoprotein E, BACE1 = beta-amyloid converting enzyme 1, BDNF = brain-derived neurotrophic factor, CD33 = sialic acid binding immunoglobulin-like lectin 3 (Siglec-3), CSF = cerebrospinal fluid, EPHA1 = erythropoietin-producing hepatoma receptor A1, NAT2 = N-acetyltransferase 2, NFL = neurofilament light, PD = pharmacodynamic, PGx = pharmacogenomics, RNA = ribonucleic acid, TREM2 = triggering receptor expressed on myeloid cells 2, VILIP1 = visinin like protein 1, YKL-40 = human cartilage glycoprotein-39 (HC gp-39)

a: mandatory for all subjects

b: to be analyzed in a subset of subjects

Biomarkers

The CSF sample will be used for PD and exploratory assessments including but not limited to CSF Aβ(1-x), Aβ(1-42), t-tau, and p-tau. (revised per Amendments 02 and 03)

The plasma sample will be used for Aβ(1-x) analysis and may be used for exploratory biomarker analyses. Aβ(1-x) in both CSF and plasma will be measured using a modified commercially available enzyme-linked immunosorbent assay (ELISA). The prescreening and postscreening analysis of CSF Aβ(1-42), t-tau, and p-tau will be performed using commercially available ELISAs. (revised per Amendments 02 and 03)

Blood samples will be collected for PD/exploratory biomarker assessments as specified in Table 4 and Table 5. (revised per Amendment 02) The blood sample collected for PD analyses at Visit 2 should be collected at fasting or at least 2 hours after the most recent meal and PD blood samples should be taken predose at Visits 3, 4, 6, 7, 9, 11, and 13 (or ED) and, as far as is feasible, samples should be taken at the same time of day. (revised per Amendment 03)

Prerandomization blood samples for immunologic assessments and CSF (if applicable) will also be stored for determination of prior exposure to any suspected infective agents in the

event that the subject develops TEAEs that warrant further investigation (eg, treatment-emergent infection). (revised per Amendments 02 and 03) Testing may include, but not be limited to, serological tests (eg, HSV1 and 2), viral titer by quantitative polymerase chain reaction (Q-PCR), and/or human leukocyte antigen (HLA) genotyping.

For all subjects, baseline and on-study blood samples, DNA samples, and any collected CSF samples (if applicable) will be stored for up to 15 years.

See the laboratory manual (to be supplied to study sites) for a description of the collection, handling, and shipping procedures of the biomarker samples.

Pharmacogenomics

A blood sample will be obtained at Screening and will be used to determine the *ApoE* genotype of all subjects enrolled in this study. NAT2 genotype will be evaluated in a subset of subjects. Genotype will be determined from blood specimens using validated assays. (revised per Amendment 03) The findings will be used in the statistical analysis to determine the effects on treatment response and safety.

The genomic DNA samples will be stored and may also be used to examine the role of genetic variability in subjects' absorption, distribution, metabolism, and excretion, the development of AEs, or underlying AD. Variations in elenbecestat exposure or the occurrence of AEs observed in the study population may be evaluated by correlation of single-nucleotide polymorphisms with PK, safety, or PD data.

Details of PGx testing may be provided and reported separately.

Amyloid PET

An amyloid PET scan may be performed at Screening to confirm deposition of amyloid in the brain. A historical amyloid positive PET scan may be used if conducted within 12 months before the planned date of randomization and provided that the scan and result are considered acceptable by the central PET reading group. As part of an optional substudy, longitudinal amyloid PET imaging will also be conducted after 12 and 24 months of treatment (or at ED, provided the subject has received at least 39 weeks of study drug and at least 6 months has elapsed since the prior amyloid PET scan was performed). (revised per Amendment 03) Longitudinal amyloid PET imaging will only be conducted on subjects that have consented to this optional substudy and who have had Screening amyloid PET scans performed for this study (ie, historical amyloid PET scans cannot be used for the longitudinal analyses).

For subjects participating in the amyloid PET substudy, amyloid PET imaging will be conducted on separate days from the scheduled visits and should be conducted before the clinic Visit 9 and no later than 7 days after the last dose for Visit 13/ED. (revised per Amendment 05)

Descriptions and detailed instructions for all amyloid PET imaging can be found in the PET imaging manual provided to the study PET imaging facilities.

Tau PET (revised per Amendment 04)

A third longitudinal biomarker substudy (tau PET) will be offered to study-eligible subjects from select geographical sites (based on proximity to the tau PET ligand manufacturing sites) in the US who have an amyloid positive study-specific PET scan and who consent to participate in the amyloid PET substudy. For subjects who consent to the tau PET longitudinal substudy, tau PET imaging will be conducted during Screening (after amyloid positive PET results have been reported and before randomization) and again at 24 months (or at the ED Visit, provided the subject has received at least 39 weeks of study drug). At the 24 month timepoint (or at the ED Visit), the amyloid and tau PET scans can be performed in either order, but must be at least 48 hours apart. If the subject has also consented to the longitudinal CSF substudy, the longitudinal substudy assessments can be performed in any order, with at least 48 hours between each procedure.

For subjects participating in the tau PET substudy, tau PET imaging will be conducted on separate days from the scheduled visits and should be conducted before clinic Visit 13/ED and no later than 7 days after the last dose of study drug. (revised per Amendment 05)

Descriptions and detailed instructions for all tau PET imaging can be found in the tau PET imaging manual provided to the study tau PET imaging facilities that will be in select geographical locations in the US, based on proximity to the tau PET ligand manufacturing sites. (revised per Amendment 04)

Further details regarding pharmacodynamics, pharmacogenomics, and other biomarker research is provided in [Appendix 4](#).

